5.2.5 Prior and Concomitant Therapy

All investigator terms for medications recorded in the CRF will be coded using the WHO Drug Dictionary (using the 2018 B2 version or later). The number (percentage) of subjects who have taken prior and concomitant antihypertensive, antidiarrheal and anthracycline medications will be summarized on the Safety Analysis Set, by the Anatomical Therapeutic Chemical (ATC) Classification, WHO drug dictionary preferred term, and by dose level in Phase 1 and by cohort in Phase 2. Other prior and concomitant medications, excluding antihypertensive, antidiarrheal and anthracycline will be summarized similarly. If a subject has taken prior and concomitant medications more than once within the same preferred term, the subject will be counted only once for the respective preferred term. Prior medications will be defined as medications that stopped prior to the first dose of study drug. Concomitant medications will be defined as medications that (i) have started before the first dose of study drug and are continuing at the time of the first dose of study drug, or (ii) have started on or after the date of the first dose of study drug up to 28 days following the last dose. Medications that cannot be determined to be prior/concomitant due to missing or incomplete dates will be regarded as concomitant (see [Section 5.3.5.2](#)).

Data listings will be provided for all prior and concomitant medications.

All other concomitant therapies or diagnostic, therapeutic, or anticancer procedures relating to malignancy, and palliative radiotherapy will also be summarized and/or listed as applicable.

5.2.6 Treatment Compliance

Not collected on CRF.

5.3 Data Analysis General Considerations

For incomplete dates involving efficacy and other safety data, a conservative imputation will be used for calculation. See [Section 8.2.1](#) for the outline of imputation rules, which will be specified in the study analysis dataset specifications with more details.

5.3.1 Pooling of Centers

Subject data from all centers will be pooled for all analyses. Center will not be considered as a factor in the analyses.

5.3.2 Adjustments for Covariates

No adjustment for covariates will be made for this study.

5.3.3 Multiple Comparisons/Multiplicity

No multiplicity adjustment will be made for this study.

5.3.4 Examination of Subgroups

Subgroup analyses may be conducted if appropriate.

5.3.5 Handling of Missing Data, Dropouts, and Outliers

5.3.5.1 Adverse Events

Adverse events with incomplete start dates will be considered as treatment emergent if:

- Day and month are missing, and the year is equal to or after the year of the first study drug dose date
- Day is missing, and the year is after the year of the first study drug dose
- Day is missing and the year is equal to the year of the first study drug dose date and the month is equal to or after the month of the first dose date
- Year is missing; or complete date is missing

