9.5.1.5.1 ADVERSE EVENTS

An AE is any untoward medical occurrence in a patient or clinical investigation subject administered an investigational product. An AE does not necessarily have a causal

relationship with the medicinal product. For this study, the study drugs are lenvatinib and everolimus.

The criteria for identifying AEs in this study are:

- Any unfavorable and unintended sign (including an abnormal laboratory finding), symptom, or disease temporally associated with the use of an investigational product, whether or not considered related to the investigational product (Note: Every sign or symptom should not be listed as a separate AE if the applicable disease [diagnosis] is being reported as an AE)
- Any new disease or exacerbation of an existing disease. However, worsening of the primary disease should be captured under efficacy assessments as disease progression rather than as an AE.
- Any deterioration in nonprotocol-required measurements of a laboratory value or other clinical test (eg, ECG or x-ray) that results in symptoms, a change in treatment, or discontinuation of study drug
- Recurrence of an intermittent medical condition (eg, headache) not present pretreatment (Baseline)
- An abnormal laboratory test result should be considered an AE if the identified laboratory abnormality leads to any type of intervention, withdrawal of study drug, or withholding of study drug, whether prescribed in the protocol or not.

All AEs observed during the study will be reported on the CRF. All AEs, regardless of relationship to study drug or procedure, should be collected beginning from the time the subject signs the study ICF through the last visit and for 28 days after the last dose of study treatment. Serious AEs (SAEs) will be collected for 28 days after the last dose of study treatment.

Abnormal laboratory values should not be listed as separate AEs if they are considered to be part of the clinical syndrome that is being reported as an AE. It is the responsibility of the investigator to review all laboratory findings in all subjects and determine if they constitute an AE. Medical and scientific judgment should be exercised in deciding whether an isolated laboratory abnormality should be classified as an AE. Any laboratory abnormality considered to constitute an AE should be reported on the Adverse Event CRF.

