5.3.5.2 Concomitant Medications

Medications will be considered concomitant if:

- Day and month are missing, and the year is equal to or after the year of the first study drug dose date
- Day is missing, and the year is after the year of the first study drug dose

- Day is missing and the year is equal to the year of the first dose date and the month is equal to or after the month of the first study drug dose date
- Year is missing; or complete date is missing

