5.6.2 Adverse Events

The adverse event (AE) verbatim descriptions (investigator terms from the eCRF) will be classified into standardized medical terminology using MedDRA version 21.1 or higher. Adverse events will be coded to the MedDRA lower level term (LLT) closest to the verbatim term. The linked MedDRA preferred term (PT) and primary system organ class (SOC) are also captured in the database.

A treatment-emergent adverse event (TEAE) is defined as an AE that had an onset date on or after the first dose of study drug up to 28 days following the last dose of study drug, or a worsening in severity from Baseline (pretreatment). In addition, if an AE reemerges during treatment, having been present at pretreatment (Baseline) but stopped before treatment, it is also counted as TEAE. The Common Terminology Criteria for Adverse Events (CTCAE) version 4.03 will be used to assess the severity of AEs.

Only those AEs that are treatment emergent will be included in summary tables. All AEs, treatment emergent or otherwise, will be presented in subject data listings. TEAEs will be summarized by dose level in Phase 1 and by cohort in Phase 2.

The incidence of TEAEs will be reported as the number (percentage) of subjects with TEAEs by SOC and PT. A Subject will be counted only once within an SOC and PT, even if the subject experiences more than 1 TEAE within a specific SOC and PT. The number (percentage) of subjects with TEAEs will also be summarized by highest CTCAE grade. The number (percentage) of subjects with treatment-related TEAEs will also be summarized by SOC and PT. Treatment-related TEAEs include those events considered by the investigator

to be related to study treatment or missing causality.

In summary, the following TEAE tables will be provided if appropriate:

- Overview of TEAEs
- TEAEs by SOC and PT
- TEAEs in decreasing frequency of PT
- TEAEs by SOC, PT, and CTCAE grade
- TEAEs with CTCAE Grades ≥ 3 by decreasing frequency of PT
- Overview of treatment-related TEAEs
- Treatment-related TEAEs by SOC and PT
- Treatment-related TEAEs by SOC, PT, and Worst CTCAE grade
- Treatment-related TEAEs by decreasing frequency of PT with CTCAE Grades ≥ 3

The number (percentage) of subjects with Grade 5 (fatal) TEAEs will be summarized by MedDRA SOC and PT and a subject data listing of all deaths (whether or not treatment emergent) will be provided. All deaths reported will also be summarized in a table.

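### SAP 5.3.5.1 ignores the stop date, so some adverse events known to have ended before first dose are counted as treatment-emergent, contrary to the definition in SAP 5.6.2

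*SAP*

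**What the plan says.** SAP 5.3.5.1 introduces its rule with "Adverse events with incomplete start dates will be considered as treatment emergent if". Four conditions follow:

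- Day and month are missing, and the start year is that of first dose or later.
- Day is missing, and the start year is later than that of first dose.
- Day is missing, the start year is that of first dose, and the start month is the same or later.
- "Year is missing; or complete date is missing".

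All four concern the start date. SAP 8.2.1 adds that partial adverse event dates are not imputed, so nothing else in the SAP settles the flag.

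SAP 5.6.2 gives three routes to treatment-emergent status. The event "had an onset date on or after the first dose of study drug up to 28 days following the last dose of study drug"; it worsened from baseline; or it re-emerged during treatment after having stopped beforehand. Only treatment-emergent events enter the summary tables.

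Protocol 9.5.1.5.1 says that all adverse events "should be collected beginning from the time the subject signs the study ICF". Screening runs from Day -28 to Day -2 (Protocol 9.1.1.1), so pre-dose events will be in the database.

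For medications, SAP 5.3.5.2 has a parallel list under "Medications will be considered concomitant if" without saying which date is incomplete. SAP 5.2.5 states "Prior medications will be defined as medications that stopped prior to the first dose of study drug" and reserves the concomitant default for medications whose status cannot be determined, with a cross-reference to 5.3.5.2.

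**The concern.** A default of treatment-emergent is sensible when the timing of an event is in doubt. A recorded stop date before first dose removes the doubt. The event was over before any drug was given, so it did not start on treatment and that episode could not worsen on treatment. If it came back later, the recurrence would be a new episode with its own onset. The rule in 5.3.5.1 and the definition in 5.6.2 then give opposite answers for the same record.

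The flag decides whether the event appears in the tables of treatment-emergent events, of Grade 3 or higher events, and of clinically significant events for lenvatinib. SAP 5.6.2 also treats missing causality as treatment-related, so a poorly completed pre-dose record could end up in the treatment-related tables. The groups are small, so a single record can change a reported percentage visibly.

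**Working it through.** The plan gives no figure on this point, so there is none to reproduce. The check applies the rule as written and compares it with the definition.

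**One record.** Start day unknown, March 2021; stop 10 March 2021; first dose 20 March 2021 (illustrative dates).

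- SAP 5.3.5.1: day missing, same year, same month. Result: treatment-emergent.
- SAP 5.6.2: the event ended 10 days before first dose, so there was no onset, worsening or re-emergence on treatment. Result: not treatment-emergent.

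**Which records are affected.** All have a recorded stop date before first dose.

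| Missing part of start date | Flagged by 5.3.5.1 | Not flagged |
|---|---|---|
| Day | Start month is the month of first dose | Start in an earlier month or year |
| Day and month | Start year is the year of first dose | Start in an earlier year |
| Year, or whole date | Always | Never |

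**Share of such events flagged.** Assumptions, not in the documents: onset is equally likely on each of the 28 days before first dose, first dose is equally likely on each day of a 365-day year, and the event ends before first dose. There are 365 × 28 = 10,220 combinations.

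- *Day missing.* With first dose on day k of a month, min(28, k − 1) of the 28 look-back days lie in that month. Summed over k, this is 462 for a 31-day month, 434 for a 30-day month and 378 for a 28-day month. The year gives 7 × 462 + 4 × 434 + 378 = 5,348, and 5,348/10,220 = 52%.
- *Day and month missing.* Onset escapes the flag only if it lies in the previous calendar year, which needs first dose on 1 to 28 January. That is 28 + 27 + … + 1 = 406 combinations, so (10,220 − 406)/10,220 = 96% are flagged.
- *Year or whole date missing.* 100%.
- *With a stop-date check added.* 0% in all three cases.

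**Effect of one record on a rate.** If the subject has no other treatment-emergent event in the same preferred term, the rate rises by 1/n:

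- 1/20 = 5 percentage points in a full Phase 2 cohort of 20;
- 1/6 = 16.7 points at a Phase 1 level of 6;
- 1/3 = 33.3 points at a level of 3.

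The shares above apply only to events that have both an incomplete start date and a known pre-dose stop. The documents do not say how many there will be, so the total effect on the tables cannot be calculated.

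**The case against.** The strongest reply is that the problem is rare and errs on the safe side. The window from consent to first dose is at most about four weeks. Worsening of the primary disease is recorded under efficacy and not as an adverse event (Protocol 9.5.1.5.1), existing conditions go to medical history, and eligibility requires recovery from the acute effects of earlier therapy. A flagged record changes a rate only if the subject has no other event in that term, because SAP 5.6.2 counts each subject once. Any error raises the count of toxicity. All of this stands, and it limits the size of the point. It does not justify the rule, because a cautious default exists to settle uncertainty and here the date is known. The SAP itself checks partial dates against other known dates elsewhere: progression and last tumor assessment against death (8.2.1.3, 8.2.1.4), subsequent therapy against last dose (8.2.1.5), and the end of prior radiotherapy against treatment start (8.2.1.6).

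A second reply is that SAP section 9 places derivation rules in separate specifications, which may contain a stop-date check. That is possible and cannot be checked from the documents. Even so, the SAP text would still conflict with its own definition.

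A reader might also infer that SAP 5.3.5.2 commits the same error for medications, so that, for example, an old anthracycline course with an unknown start and a known pre-dose end would be tabulated as concomitant. The documents do not support this. SAP 5.2.5 makes a medication that stopped before first dose prior and sends only undeterminable cases to the concomitant default. A known pre-dose stop makes the case determinable. What remains is that 5.3.5.2 does not name the date that it tests.

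**Conclusion.** For adverse events the rule is wrong as written. For a definable set of records SAP 5.3.5.1 yields a classification that SAP 5.6.2 rules out. It would go too far to say that every event that ended before first dose is counted: a partial start in an earlier month (day missing) or an earlier year is not flagged.

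The point is minor. The direction is over-counting, the number of records is unknown and may be zero, and each record adds at most 1/n to a rate. The 52% and 96% shares rest on the uniform-timing assumptions stated above; the 100% and 0% do not. The Phase 2 response rate does not use this flag, and DLTs are determined by the investigator and the medical monitor from Cycle 1 events attributable to the study drugs. For medications the documents show unclear wording, not a contradiction.

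**What to change.** Add one exception to SAP 5.3.5.1 covering all four conditions: *unless the complete or partial stop date shows that the event ended before the first dose of study drug*. Keep the treatment-emergent default when the stop date is missing, ongoing, too incomplete to decide, or on or after first dose.

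In SAP 5.3.5.2, at most align the wording: name the date meant and refer back to 5.2.5, under which a known pre-dose stop makes the medication prior.

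The cost is one sentence in 5.3.5.1, an optional clarification in 5.3.5.2 and one programming condition. Nothing is lost, because records whose timing is unresolved stay in the safety tables. If the dataset specifications already contain the check, only the SAP text needs to change.

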5.3.5.2 Concomitant Medications

Medications will be considered concomitant if:

- Day and month are missing, and the year is equal to or after the year of the first study drug dose date
- Day is missing, and the year is after the year of the first study drug dose

- Day is missing and the year is equal to the year of the first dose date and the month is equal to or after the month of the first study drug dose date
- Year is missing; or complete date is missing

5.3.6 Other Considerations

5.3.6.1 BSA Dose Adjustment and Dose Capping

Subjects in Phase 1 will receive study drug as described in Protocol Section 9.1, Tables 3 (lenvatinib) and 4 (everolimus).

The actual dose level of lenvatinib and everolimus could be different from the planned dose level due to the adjustment of BSA and dose capping. The actual dose level of lenvatinib and everolimus will be calculated from actual daily dose and BSA. The subject with dose capping will be listed. For Phase 1 and Phase 2 the planned dose level will be used for column grouping across all analyses.

5.3.6.2 Summarization of Safety Data

Regarding summarization of mean and mean change from Baseline for laboratory, vital sign, and ECG data, if 2 or fewer subjects in each of the treatment groups have data for a given cycle, the applicable cycle(s) will not be summarized, and the table will be curtailed. For example, if at Cycle 10 the 3 treatment groups have 4, 3 and 1 subjects, respectively, then Cycle 10 will be summarized for all treatment groups. If at Cycle 11, the 3 treatment groups have 2, 2 and 1 subject, respectively, and at subsequent cycles no treatment has 3 or more subjects, then the table will not be produced for Cycle 11 and all subsequent cycles. However, for shift tables and other analyses of worst postbaseline values, all data will be included.

5.4 Primary, Secondary and Exploratory Analyses

5.4.1 Primary Analyses

5.4.1.1 Dose-Finding Analysis in Phase 1

The primary objective of Phase 1 is to determine the MTD and to establish RP2D of lenvatinib administered in combination with everolimus. The study will utilize the rolling 6 design detailed in SAP [Section 3.2](#).

5.4.1.2 Primary Efficacy Analysis for Phase 2

Efficacy analyses for Phase 2 will be performed separately for each study cohort.

The primary objective of Phase 2 is to estimate the antitumor activity of lenvatinib in combination with everolimus in pediatric subjects with Ewing sarcoma/peripheral primitive neuroectodermal tumor (pPNET), rhabdomyosarcoma, and HGG using the ORR at 16 weeks. The ORR at Week 16 is defined as the proportion of subjects who have the BOR of CR or PR at Week 16.

Subjects must have measurable disease present at baseline for Phase 2. Those who have their disease re-evaluated at postbaseline visits will be considered evaluable for objective response. Estimated ORR and its exact 95% CI using the Clopper-Pearson [Clopper and Pearson, 1934] method will be presented.

The data cutoff for the primary study analysis in Phase 2 will occur when all evaluable subjects have completed at least 4 treatment cycles and, if applicable, a confirmatory scan has been performed (in case of a PR or CR at Week 16), or have discontinued study treatment early.

Tumor response data utilized in the primary analysis of ORR will be obtained from investigator's assessment of the imaging scans. No independent tumor assessments will be performed as part of this study. Tumor response will be assessed by RECIST 1.1 criteria [Eisenhauer, et al., 2009] in pediatric subjects with Ewing sarcoma/peripheral primitive neuroectodermal tumor (pPNET) and rhabdomyosarcoma, and RANO criteria will be used for subjects with HGG [Wen, et al., 2010]. Efficacy analyses in Phase 2 will primarily be based on the Evaluable Analysis Set .

The BOR is determined once all data for a subject is known. For this study, a confirmation of CR or PR is required for both RECIST 1.1 and RANO. The confirmation assessments should be made ≥ 4 weeks after the initial response assessment. The BOR is determined by sequentially checking two adjacent assessments (≥ 4 weeks apart).

5.4.2 Secondary Efficacy Analyses

5.4.2.1 Phase 1

The secondary efficacy analyses in Phase 1 subjects will be summarized by planned dose level and overall if appropriate and listed by dose level group and based on the Safety Analysis Set. Subjects with measurable disease (target lesions at baseline with or without nontarget lesions at baseline) and evaluable disease (only nontarget disease at baseline) will be summarized separately for their best overall response. The response will be classified according to RECIST 1.1 and RANO defined categories for subjects.

- BOR will be analyzed separately for subjects with measurable disease and for subjects with only evaluable disease.
 - To be assigned a best overall response of SD (measurable disease), Non-CR/Non-PD or IR/SD (evaluable disease), the time from the first administration of study drug until the date of documented SD, Non-CR/Non-PD, or IR/SD should be ≥ 7 weeks. IR/SD is Incomplete Response/Stable Disease from RANO.
- ORR at the time of cut off: defined as the proportion of subjects with measurable disease at screening/baseline achieving a best overall response of confirmed PR or CR at the time of data cutoff. ORR will be estimated by dose level, and by exact Clopper-Pearson 95% CI if appropriate.

- DCR: For subjects with measurable disease, defined as the proportion of subjects who achieved a best overall response of CR, PR, or SD (minimum duration of SD ≥ 7 weeks). For subjects with evaluable disease, defined as the proportion of subjects:
 - those assessed by RECIST 1.1 who have a BOR of CR, or Non-CR/Non-PD ≥ 7 weeks
 - those assessed by RANO who have a BOR of CR, or IR/SD ≥ 7 weeks.

The count and percentage will be summarized by dose level, and by exact Clopper-Pearson 95% CI if appropriate.

- Clinical Benefit Rate (CBR): For subjects with measurable disease, defined as the proportion of subjects with measurable disease who have a BOR of CR or PR, or durable SD lasting ≥ 23 weeks. For subjects with evaluable disease, defined as the proportion of subjects:
 - those assessed by RECIST 1.1 who have a BOR of CR, or Non-CR/Non-PD lasting ≥ 23 weeks,
 - those assessed by RANO who have a BOR of CR, or IR/SD lasting ≥ 23 weeks.

The count and percentage will be summarized by dose level, and by exact Clopper-Pearson 95% CI if appropriate.

- DOR: defined as the time from the date of first documented confirmed CR or PR to disease progression objectively documented or death (whichever comes first). The DOR will be analyzed using the Kaplan-Meier (KM) ([Kaplan and Meier, 1958](#)) method among the responders (CR or PR). The DOR will be analyzed using the KM approach among the responders (CR or PR) according to the rules in [Table 3](#).

5.4.2.2 Phase 2

Subjects must have measurable disease at baseline for enrollment in Phase 2. The secondary efficacy endpoints ORR at the time of data cutoff, DCR, CBR and DOR will be performed for subjects in the Evaluable Analysis Set.

- ORR at the time of data cutoff: defined as the proportion of subjects achieving a best overall response of confirmed PR or CR at the time of data cutoff. ORR and corresponding exact 95% CI using the Clopper-Pearson method will be estimated for all Phase 2 treatment disease cohorts.
- DCR: defined as the proportion of subjects who have a BOR of CR or PR or stable disease (SD). To be assigned a best overall response of SD, the time from the first dose of study treatment until the date of documented SD should be ≥ 7 weeks. The count and percentage with exact Clopper-Pearson 95% CI for the DCR will be summarized for all Phase 2 treatment disease cohorts.
- CBR: defined as the proportion of subjects with who have a BOR of CR or PR or durable SD lasting ≥ 23 weeks. The count and percentage with exact Clopper-Pearson 95% CI for the CBR will be summarized for each Phase 2 treatment disease cohort.

- DOR: defined as the time from the date of first documented confirmed CR or PR to disease progression objectively documented or death (whichever comes first). The DOR will be analyzed using the Kaplan-Meier (KM) ([Kaplan and Meier, 1958](#)) method among the responders (CR or PR) according to the rules in [Table 3](#).

• Table 3 DOR and Censoring Rules			
No.	Situation	Date of Progression or Censoring	Outcome
1	Progression documented between scheduled visits, on or prior to new anticancer therapy	Date of first radiologic PD assessment	PFS Event
2	No progression at the time of data cutoff	Date of last adequate radiologic assessment on or prior to data cutoff	Censored
3	New anticancer therapy started before the first PD or death	Date of last adequate radiologic assessment on or prior to the start of new anticancer therapy	Censored
4	Death before first PD assessment, on or prior to start of new anticancer therapy	Date of death	PFS Event
5	Death between adequate assessment*	Date of death	PFS Event
6	Death or progression after more than one missed visit/tumor assessment**	Date of last adequate radiologic assessment before missed tumor assessments	Censored

Note:
 
* Adequate tumor assessment is radiologic assessment at regular interval as defined in the protocol.
 
** More than 1 missed visit/adequate tumor assessment of subjects is defined as having the duration between the last adequate tumor assessment and PD or death being longer than 125 days in Treatment Phase of Phase 2 and longer than 181 days in Extension Phase for both Phase I and II.
			

If a subject had PFS event (#1, #4 or #5), the earliest event date will be used.

The priority of the censoring rules is described as follows:

- If a subject missed two or more tumor assessments before PD or death (#6), the subject will be censored at the date of the last adequate tumor assessment before the missed tumor assessments.
Note that if a subject is censored by both this criterion and start of new anticancer therapy criterion, the earliest censoring date will be used.
- If a subject did not have PD or death, the censoring date will be the earliest censoring date if the subject met multiple censoring criteria (#2, #3, #6).

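### SAP Table 3 row 5 omits the new-therapy condition of rows 1 and 4, so some responder deaths after new therapy are both censored (row 3) and an event (row 5) for duration of response

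*SAP*

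**What the plan says.** SAP Section 5.4.2 estimates duration of response (DOR) by Kaplan-Meier among responders, in both phases, using the rules in Table 3. The rows that matter are:

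- Row 1, event: "Progression documented between scheduled visits, on or prior to new anticancer therapy".
- Row 3, censored at the last adequate scan on or before the new therapy: "New anticancer therapy started before the first PD or death".
- Row 4, event at death: "Death before first PD assessment, on or prior to start of new anticancer therapy".
- Row 5, event at death: "Death between adequate assessment".
- Row 6, censored: death or progression after more than one missed assessment. The footnote defines this as a gap since the last adequate assessment that is "longer than 125 days in Treatment Phase of Phase 2 and longer than 181 days in Extension Phase".

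The text under the table adds three statements:

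- On events: "If a subject had PFS event (#1, #4 or #5), the earliest event date will be used".
- On row 6: "Note that if a subject is censored by both this criterion and start of new anticancer therapy criterion, the earliest censoring date will be used".
- On subjects without an event: "If a subject did not have PD or death, the censoring date will be the earliest censoring date", where rows 2, 3 and 6 are the criteria listed.

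Protocol 9.7.1.6.2 censors at the last available tumor assessment a responder with no progression or death before early discontinuation, and it names change of cancer treatment among the discontinuation reasons. SAP Section 7 states that the planned analyses are unchanged from the protocol.

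**The concern.** Rows 1 and 4 stop counting events once new anticancer therapy begins, and row 3 is the matching censoring rule. Row 5 lacks the limit. A responder who moves to another treatment without documented progression and dies soon afterwards therefore fits a censoring row and an event row at once, and the priority text does not choose between them.

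Such records can arise. Survival is followed every 3 months for up to 1 year (SAP 3.2.6.1). Anticancer therapy is recorded until death or the end of survival follow-up (protocol Tables 7 and 8, footnote v).

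If the event is used, DOR for these responders includes time and death under another treatment. A responder who dies slightly later falls under row 6 and is censored. The outcome would then turn on the gap since the last scan and on how a programmer resolved the ambiguity.

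**Working it through.** **The row 6 limits.** The SAP gives no formula for them, but they match two scan intervals plus two 7-day windows, less 1 day: 2×56 + 2×7 − 1 = 125 and 2×84 + 2×7 − 1 = 181. This is a reconstruction. The limits bound the conflict, because beyond them row 6 censors.

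**Rows met by a responder without progression who dies.** The last adequate scan is day 0. Row 5 is taken as met whenever the gap is within the row 6 limit.

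| New therapy | Death | Rows met | Outcome |
|---|---|---|---|
| none | day 60 | 4, 5 | event |
| day 20 | day 60 | 3, 5 | censored and event |
| day 20 | day 125 (181 in Extension) | 3, 5 | censored and event |
| day 20 | day 126 (182 in Extension) | 3, 6 | censored |

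**The priority text.** The event sentence names row 5 with no exception for row 3. The new-therapy criterion then appears twice: jointly with row 6, and for subjects who had neither progression nor death. The subject in the second and third lines of the table fits neither case, so nothing in the text ranks row 3 against row 5.

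**Row 5 is not mere repetition of row 4.** If the first PD assessment in row 4 means first documented progression, row 4 already covers every death before progression and before new therapy. Row 5 then adds only deaths after new therapy. If it means the first scheduled scan, row 4 cannot apply to a confirmed responder, and row 5 governs responder deaths without the limit.

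**Constructed record.** PR at week 8, PR at week 16 (confirmed), new therapy at week 20, death at week 22. The gap from last scan to death is 22 − 16 = 6 weeks = 42 days, below 125, so row 6 does not apply.

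- Row 3: censored at 16 − 8 = 8 weeks.
- Row 5: event at 22 − 8 = 14 weeks.

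**Effect on a small curve.** At the 25% alternative with 20 evaluable subjects, 0.25 × 20 = 5 responders are expected, so one record is 1/5 = 20% of the DOR data. Take four responders with events at days 112 and 168 and censoring at days 252 and 336, counted from first response. The fifth has a last scan at day 56, new therapy at day 100 and death at day 140 (gap 84 days).

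- Fifth censored at day 56: S(112) = 3/4 = 0.75; S(168) = 0.75 × 2/3 = 0.50. Two events.
- Fifth an event at day 140: S(112) = 4/5 = 0.80; S(140) = 0.80 × 3/4 = 0.60; S(168) = 0.60 × 2/3 = 0.40. Three events.

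The first time the curve is at or below 0.50 is day 168 in both cases.

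**With row 4's condition added to row 5,** these deaths meet row 3 alone (within the limit) or rows 3 and 6 (beyond it). Both are censoring, so the conflict disappears.

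**The case against.** The best counter-case is that the plan already implies censoring.

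- The event sentence selects among event dates. It does not place events above censoring.
- Row 3's own wording anticipates a later progression or death and still censors. The row 6 note also applies the new-therapy criterion to subjects who had an event.
- Protocol 9.7.1.6.2 and SAP Section 7 point the same way.
- Protocol 9.5.1.3.1 requires scans after discontinuation only until progression or a new anticancer agent. A death after new therapy may therefore not lie between adequate assessments at all, which would empty row 5 for these subjects.
- SAP Section 9 puts derivation rules in separate documents, which may already settle the point.

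Most of this stands as evidence of intent, and it is why a reader who infers that the SAP ranks the event above censoring goes too far: no sentence says so. It does not remove the defect. The narrow reading of row 5 is nowhere stated, the event sentence names row 5 without exception, and rows 1 and 4 show that the authors wrote the condition where they wanted it.

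The objection on size also stands. The records above are constructed, the documents give no frequency for such deaths, and the share of 1 in 5 is not an effect on an estimate.

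**Conclusion.** Row 5 conflicts with row 3 for a defined set of deaths: responders without progression who start new anticancer therapy and die within 125 days (Phase 2 Treatment Phase) or 181 days (Extension Phase) of the last adequate scan. The priority text leaves the conflict open. Its literal reading permits the event, while row 3 and the protocol point to censoring.

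Three stronger inferences are not supported. The conflict does not cover every death on later therapy, because row 6 censors beyond the limits. A change in median DOR has not been shown; only the event count and the curve changed in the example. The primary ORR and the cohort stopping and failure rules use response counts, so they are unaffected.

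The impact is on one secondary, descriptive endpoint with few responders per cohort. The conclusion assumes that a death within the row 6 limit can fall under row 5 even when no later scan was due.

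**What to change.** In SAP Table 3, add to row 5 the new-therapy condition that row 4 already carries. In the priority note, state that row 3 takes precedence over row 5: a death after the start of new anticancer therapy is not a DOR event and is censored under row 3. Rows 1 and 4 need no change, since both already carry the condition and ranking row 3 above them would be redundant. Check any separate derivation specification against the revised wording. The cost is a few words in the table and its note, with no new data.
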